## 1 List of Abbreviations

Abbreviation	Abbreviation definition
BWHS	Black Women's Health Study
GLMM	General Linear Mixed Model
CBT-I	Cognitive-behavioral therapy for insomnia
ISI	Insomnia Severity Index
SOL	Sleep Onset Latency, i.e., time awake before first falling asleep
SHUTi	Sleep Healthy Using the Internet
SHUTi-BW	modified SHUTi six-module program tailored for Black women
WASO	Wake After Sleep Onset, i.e., amount of time awake after first falling asleep

## 2 Protocol Summary

Title:	Reducing Health Disparities for Black Women in the Treatment of Insomnia
Population:	Participants in the Black Women's Health Study (BWHS) who reported symptoms of insomnia on the 2015 follow-up questionnaire ages 45-85 who have internet access via a computer or laptop and provide informed consent for participation.
Intervention:	For drugs: name, dose, route of administration, regimen; for other interventions: name, method, timing.
Objectives:	The goal of this study is to conduct a comparative effectiveness trial of three internet-based intervention approaches to insomnia treatment to assess which of these insomnia interventions are most effective for Black women: 1) patient education (PE) which is usual care (website providing sleep hygiene information) 2) standard SHUTi six-module program 3) modified SHUTi six-module program tailored for Black women, i.e., SHUTi-BW
Design/Methodology:	A single-blind (participants), parallel randomized clinical trial among eligible Black women with insomnia, using an equal allocation ratio. Participants will be randomized to 1 of 3 groups: patient education (PE) (sleep hygiene information), Sleep Healthy Using the Internet (SHUTi - a cognitive behavioral therapy for insomnia (CBT-I) program), or SHUTi modified for Black women. Participants will be randomized to patient education (also called sleep hygiene or sleep information) will use a website that discusses ways to improve behaviors and environments that can affect sleep.
Total Study Duration:	Total study duration is expected to be about 24 months.
Subject Participation Duration:	Individual participant duration is approximately 9 months.

## 3 Background/Rationale & Purpose

### 3.1 Background Information

Black women are at a higher risk of developing insomnia and insomnia has profound adverse physical and psychological health consequences, including cardiovascular disease, diabetes, and anxiety. There is a non-pharmacological internet-based self-administered treatment for insomnia called SHUTi (Sleep Healthy Using the Internet) that has been shown to be effective in multiple randomized trials among populations that were predominantly white. There were few Black participants and there is little evidence of the effectiveness of this treatment among Black women; specifically, the few Black women in the trials were less likely to finish the treatment program than other participants, though those that finished had improvement similar to that of other participants who finished.

This study aims to provide the much-needed evidence to assess how three different internet-based insomnia interventions affect insomnia symptoms in Black women which will help Black women make informed decisions regarding treatment for their insomnia. The three interventions are:

- 1) patient education or usual care (website providing sleep hygiene information)
- 2) standard SHUTi six-module program
- 3) modified SHUTi six-module program tailored for Black women, i.e., SHUTi-BW

This study will be conducted in compliance with the protocol, applicable regulatory requirements, and BMC/BU Medical Campus Human Research Protection policies and procedures.

### 3.2 Rationale and Purpose

This study aims to fill a gap in treating insomnia by providing evidence-based interventions to help Black women make informed decisions regarding treatment for their insomnia.

## 4 Objectives

### 4.1 Study Objectives

The goal of this study is to conduct a comparative effectiveness randomized trial of three internet-based intervention approaches to insomnia treatment to assess which of these insomnia interventions are most effective:

- 1) patient education (usual care) (website providing sleep hygiene information)
- 2) standard SHUTi six-module program
- 3) modified SHUTi six-module program tailored for Black women, i.e., SHUTi-BW

We will develop the modified SHUTi program, SHUTi-BWHS with the aid of a stakeholder group that includes Black women, a sleep physician who treats patients with sleep problems at a hospital that serves large numbers of minority patients, sleep experts, and leaders of the randomized trial. Each member of the group will work through the SHUTi cores and be interviewed after each core for suggestions on how to make the program more relevant to Black women. Based on the consensus of the stakeholder group, SHUTi will be modified to with specific sleep problems of Black women in mind.

### 4.2 Study Outcome Measures

#### 4.2.1 Primary Outcome Measures

The primary study outcome measure will be insomnia severity, assessed with the Insomnia Severity Index (ISI). The ISI is a 7-item questionnaire well-validated in insomnia research in multiple patient populations, including in Black women. Total scores range from 0 to 28, with those scoring <8 considered to not have clinically significant insomnia symptoms; a score of 15 or greater is compatible with having insomnia disorder. An ISI score reduction of >7 points is considered a clinically significant improvement in insomnia symptoms

#### 4.2.2 Secondary Outcome Measures

Secondary sleep outcomes will include:

- time taken to fall asleep (sleep onset latency)
- time awake after falling asleep (wake after sleep onset)
- total sleep duration
- total time in bed, and
- sleep efficiency (total sleep duration divided by total time in bed, multiplied by 100)
- for participants in SHUTi or SHUTi-BWHS, engagement with the program, measured by %completing all 6 Cores.

These data will be collected via online sleep diaries.

Another secondary outcome measure will be overall sleep quality which will be assessed by the Pittsburgh Sleep Quality Index (PSQI), a 19-item survey that has been validated extensively, including among Black women.

### 5 Study Design

We will implement a single-blind (participants), parallel randomized clinical trial among eligible Black women with insomnia, using an equal allocation ratio. Participants will be randomized to 1 of 3 groups: patient education (usual care -sleep hygiene information), Sleep Healthy Using the Internet (SHUTi - a cognitive behavioral therapy for insomnia (CBT-I) program), or SHUTi modified for Black women SHUTi-BWHS. Participants randomized to patient education (also called sleep hygiene or sleep information) will use a website that discusses ways to improve behaviors and environments that can affect sleep.

### 6 Potential Risks and Benefits

#### 6.1 Risks

We will minimize the potential risks to participants by:

We will train staff to maintain a sensitive and responsive approach to speaking with participants.

*Confidentiality concerns:* In order to minimize any risks of loss of confidentiality, participants will be identified by coded study number. The file linking this coded study number to patient identifiers will be stored in a password protected database available only to relevant members of the study team involved

in direct contact with participants. The data collected via the Internet will be obtained through secured means and stored on secure servers at the University of Virginia. All data on the servers are password protected and limited to authorized research personnel. The University of Virginia study team has previously worked out a system with their prior Internet intervention studies in which two servers have been set up with one private server configured behind the HIPAA compliant firewall where secured data resides and only individuals who have onsite or VPN access are able to connect to this server. A second server maintains the front-end web system so that individuals (the participants) offsite can access the program. Data submitted by these users are captured and transferred to the secure server. Analyses will be conducted without identifiers.

*Concerns about using an internet program:* participants will be instructed to contact study staff if they have any concerns or questions about the on-line program. They are invited to contact study staff through either email or phone calls.

*Concerns about answering personal questions:* BWHS participants have provided personal data for 24 years in the BWHS. If they have concerns, they can call the project coordinator who will explain the safeguards for the data.

*Initial tiredness:* Participants who follow recommendations to restrict sleep could initially feel more tired. To minimize the risk associated with sleep restriction, the SHUTi system does not recommend that participants restrict sleep beyond the total amount of sleep the participant is already getting (based on diary data). We will instruct participants that they may contact us if they have significant concerns. As needed, we will instruct participants to contact their primary care provider or seek professional help at a sleep clinic.

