## 8 Study Intervention

The study interventions will be determined by the treatment arm to which the participant is randomized and are summarized below.

- 1) Patient education (website providing sleep hygiene information) In this active control arm randomized participants will receive 'usual care' which will include internet-delivered patient education materials about sleep. The PE website focuses on symptoms of insomnia, the impact, prevalence, and causes of insomnia, considerations on when to see a doctor, and basic lifestyle, environmental, and behavioral strategies to improve sleep.
- 2) Standard SHUTi six-module program- SHUTi. This is an automated intervention that will be delivered over six sessions/modules, each lasting approximately 45-60 minutes. SHUTi tailors content based upon each participant's reported baseline sleep function, treatment adherence, and sleep progress. It incorporates all core elements of cognitive-behavioral therapy for insomnia (CBT-I).
- 3) SHUTi-BWHS (modified SHUTi six-module program tailored for Black women) We will develop this tailored version of SHUTi over a course of one year. The development will include an iterative process between the study investigators and key stakeholders such as Black women with a history of insomnia, a BWHS participant, a sleep physician from a medical center which serves a diverse patient population, and sleep researchers.

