At this point, the BWHS Project Coordinator will enroll participants by entering their email and study ID into the SHUTi Administrative site. The BWHS Project Coordinator will be responsible for SHUTi program administration during the clinical trial. The SHUTi program will maintain contact with the woman through regular emails until the end of the woman's participation, as described below. Participants needing help will contact BWHS via email ([contact]) or the BWHS toll free number [contact]) posted on the SHUTi website. At the end of each woman's participation, the data she has supplied (ISI scores, etc.) will be transferred from the SHUTi database to BWHS. None of the data collected will have identifiers such as names and addresses.

Once a participant is enrolled, she will be sent a Welcome email with instructions for setting her password. Enrolled participants will login and complete an online Questionnaire (attached to this IRB application as "Pre-Assignment Questionnaire") asking about her health, sleep habits, and daily life activities (approximately 30-45 minutes). Participants will receive reminder emails to complete the Questionnaire.

After completing the Pre-Assignment questionnaire, participants will advance to the Sleep Diary phase. Participants will record their sleep online by entering Sleep Diaries (2 minutes to complete each) during the next two weeks. Participants must complete at least 10 diaries in those two weeks to complete this

phase with success. Participants will receive daily email reminders to complete the Sleep Diaries. A sample Sleep Diary is attached to this IRB application as "SHUTi Sleep Diary".

After a participant has completed both the Pre-Assignment Questionnaire and 10 Sleep Diaries in a two-week time period, the program automatically advances the participant to the treatment phase. Via email, participants will be directed to 1 of the 3 study programs to which they have been randomly assigned. For the next nine (9) weeks, each participant will use her assigned study website.

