### *SHUTi (Sleep Healthy Using the Internet)*

The other 2 treatment programs, Sleep Healthy Using the Internet (SHUTi), and a modification of SHUTi designed for Black women called SHUTi-BWHS, will involve participation in online treatment programs that have six modules called Cores. Each participant will log in to the six modules of her assigned treatment program over a 6 to 8-week period. Participants will use a website program designed to provide tailored instructions about how to improve their sleep. Cores are completed one at a time in order. Each Core is expected to take 45 to 60 minutes to complete. Each Core contains information and exercises designed to help change behaviors and thoughts that can contribute to sleep problems. Participants will receive automated emails encouraging them to complete tasks. Participants will be asked to complete weekly to dos and enter daily Sleep Diaries to track their sleep. After each module, participants will need to complete 5 sleep diaries to proceed to the next module (2 minutes to complete each).

Nine weeks after she completes the initial (Pre-Assignment) questionnaire, regardless of which treatment program she is assigned to, the participant will be asked to complete a Post-Assignment questionnaire about her sleep and health (45 minutes) and she will be asked again to complete 10 sleep diaries. The Post-Assignment Questionnaire will include the same questions asked at the beginning and additional evaluation questions. Six months later, participants will be asked again to complete a questionnaire, including evaluation questions, (45 minutes) and 10 sleep diaries. These three questionnaires are attached to this IRB application as Pre-Assignment Questionnaire, Post-Assignment Questionnaire and 6 Month Follow-up Questionnaire.

Participants can continue to use their assigned website between the two post treatment questionnaires.

After participants have finished their assigned program for the research, they may choose to take one of the other insomnia treatment programs. It will be offered free of charge but it will not be counted as part of this research.

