The SHUTi program has 6 cores that include behavioral, educational, and cognitive components. Most cores contain "vignettes" or stories about the sleep problems of specific (fictional) individuals, that may be presented in videos or written material with the names and faces of a variety of (fictional) men and women, of whom one is a Black woman. Some of the cores contain advice from sleep experts (mostly actors playing those roles). This will be revised to make SHUTi-BWHS with the advice of the stakeholder team.

Core 1 provides an overview and rationale for the treatment.

Cores 2 and 3 are behavioral cores that provide rules for sleep restriction and stimulus control. Rules are provided to regulate the sleep-wake schedule and strengthen the connection between the bedroom and sleep. Stimulus control means going to bed only when sleepy, getting out of bed when unable to sleep and returning to bed when sleepy, and curtailing other activities in the bedroom (e.g., reading, television). Sleep restriction means limiting the time spent in bed to increase sleep efficiency (amount of time in bed spent sleeping).

Core 4 focuses on improving sleep hygiene practices (e.g., avoiding alcohol before bedtime).

Core 5, the cognitive core, addresses unhelpful beliefs about sleep (e.g., the belief that a certain number of hours of sleep are required).

Core 6, the last core, integrates the various elements and presents strategies to prevent relapse.

SHUTi-BWHS will have the same structure and elements as SHUTi. The vignettes will be changed, so that Black women will be the characters of interest. The vignettes will also contain material that was not covered in SHUTi, such as sleep problems resulting from housing that is not quiet or that may require room sharing. The "experts" will be Black physicians. . The changes will be made with the advice of a stakeholder team that includes Black women from the community who have sleep problems, a Black community advocate, a sleep expert, a physician who treats individuals with sleep problems, and the co-PIs of this study.

This table summarizes by study week what will happen in this randomized trial.

Step	Week	Study Phase	What happens during this phase	Time required
1	1-2	Pre assignment	Complete Pre- Assignment Questionnaire  Enter 10 sleep diaries in 14 days	30 minutes  2 minutes each
2	3-12	Treatment 9 weeks	Use assigned website	

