## 10.2 Reporting Plans

The Principal Investigator at BU Medical Campus will report Unanticipated Problems, safety monitors' reports, and Adverse Events to the BMC/BU Medical Center IRB in accordance with IRB policies:

- Unanticipated Problems occurring at BMC/BU Medical Campus involving a fatal or life-threatening event will be reported to the IRB within 2 days of the investigator learning of the event.
- Unanticipated Problems occurring at BMC/BU Medical Campus not involving a fatal or life-threatening event will be reported to the IRB within 7 days of the investigator learning of the event.
- Reports from safety monitors with recommended changes will be reported to the IRB within 7 days of the investigator receiving the report.
- Adverse Events (including Serious Adverse Events) will be reported in summary at the time of continuing review, along with a statement that the pattern of adverse events, in total, does not suggest that the research places subjects or others at a greater risk of harm than was previously known.
- Reports from safety monitors with no recommended changes will be reported to the IRB at the time of continuing review.

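### The plan describes no solicited harm question and no harm table by arm, so the adverse-event summary appears to rest on what participants volunteer

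*Combined protocol and SAP*

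**What the plan says.** **The risk and its protections.** Section 6.1 states: "Participants who follow recommendations to restrict sleep could initially feel more tired". It limits restriction to the sleep a woman already gets according to her diary, and it allows referral to primary care or a sleep clinic as needed. For detection it offers this: "We will instruct participants that they may contact us if they have significant concerns". Section 9 repeats the route: women needing help email or telephone the study. Section 7.2 screens out, among others, unstable medical conditions, unmanaged sleep disorders other than insomnia, and jobs where restricted sleep could put other people in danger.

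**Where restriction occurs.** Section 9 says: "Cores 2 and 3 are behavioral cores that provide rules for sleep restriction and stimulus control". Both SHUTi programs share this structure; patient education does not include it.

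**Data flow.** Section 8 says: "SHUTi tailors content based upon each participant's reported baseline sleep function, treatment adherence, and sleep progress". The program therefore uses diary data during treatment. Section 9 says: "At the end of each woman's participation, the data she has supplied (ISI scores, etc.) will be transferred from the SHUTi database to BWHS". Section 6.1 adds: "All data on the servers are password protected and limited to authorized research personnel".

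**Adverse events.** Section 10.1 defines them broadly, related or not. Section 10.2 says: "Adverse Events (including Serious Adverse Events) will be reported in summary at the time of continuing review". It also mentions safety monitors' reports, without describing what the monitors review.

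**Outcomes.** Sections 4.2 and 12.2 cover ISI, diary measures, PSQI and program completion. No harm outcome is listed.

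**The concern.** Sections 10.1 and 10.2 govern events once they are known. They do not say how events are found. If the only source is a woman's decision to make contact, the counts depend on who chooses to report as well as on who was harmed.

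That matters most for comparing arms. In the two SHUTi arms women work through six Cores, enter daily diaries, must complete five diaries to move on, and receive automated prompting emails. In patient education they log in as they wish, with no time requirement. Readiness to report a problem could differ between arms for that reason alone, in a direction that cannot be predicted.

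Section 3.2 says the trial should help Black women make informed treatment decisions. That choice needs tolerability beside benefit. Two of the three arms, 2 × 101 = 202 of 303 women aged 45-85, are assigned a program containing sleep restriction. Marked sleepiness, falls and drowsy driving are plausible consequences. Only tiredness is named in the documents; the others are this review's clinical assumption.

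**Working it through.** **1. How could staff learn of a harm?** Setting the sections side by side:

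| Place | What it provides | Does it solicit harm? |
|---|---|---|
| 6.1 | Diary-based limit on restriction | No; it reduces risk |
| 6.1 and 9 | Participant may contact staff | No; volunteered |
| 6.1 | Referral as needed | No; follows a known problem |
| 9 | Automated emails | None described; they prompt tasks |
| 9 | Post-Assignment and 6-month questionnaires | Not described; forms not in the documents |
| 10.2 | IRB reporting, safety monitors' reports | No; concerns known events |
| 4.2, 12.2 | ISI, diaries, PSQI, completion | No harm outcome |

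ISI and diary data could show worsening sleep, but they are planned as efficacy outcomes, and no harm analysis of them is specified.

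**2. Is there a place to ask?** Yes. The first follow-up questionnaire falls due at the same time in every arm: "Nine weeks after she completes the initial (Pre-Assignment) questionnaire, regardless of which treatment program she is assigned to". The 6-month questionnaire also goes to all arms.

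**3. How long is the recall?** Assume that Core 1 starts when treatment starts and that the six Cores are evenly spaced over the stated 6 to 8 weeks, so each takes 1 to 1.33 weeks.
- Text of section 9, in weeks after the initial questionnaire: treatment starts at 2, Core 2 at 3 to 3.33, questionnaire at 9. Gap: 9 − 3.33 = 5.7 to 9 − 3 = 6 weeks.
- Section 9 table: treatment starts at week 3, Core 2 at 4 to 4.33, questionnaire at week 12. Gap: 12 − 4.33 = 7.7 to 12 − 4 = 8 weeks.

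The first answers would look back about 6 to 8 weeks to the start of restriction.

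**4. What precision would a table by arm have?** Section 12.1 gives 101 per arm and 28% attrition: 101 × 0.72 = 72.7, which agrees with its stated 72. Taking 72 responders in each of the three arms, and a common frequency p (assumed, since the documents give none), the 95% half-width for a pairwise difference is 1.96 × √[p(1 − p)(1/72 + 1/72)].

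| Assumed p | Standard error | Half-width (points) |
|---|---|---|
| 5% | √(0.0475 × 2/72) = 0.0363 | 7.1 |
| 10% | √(0.09 × 2/72) = 0.0500 | 9.8 |
| 20% | √(0.16 × 2/72) = 0.0667 | 13.1 |

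With zero events in an arm of 72, the one-sided upper 95% bound is 1 − 0.05^(1/72) = 4.1%. This precision supports description. It would not settle small differences.

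**The case against.** **The questionnaires are unseen.** They ask about health, and the later ones add evaluation questions. They may already contain harm items. This stands: the documents support 'not described', and a reader who infers that harms are not asked about at all goes too far. A table by arm would still be unplanned.

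**Earlier access is possible.** A reader might infer from the end-of-participation transfer that staff see none of a woman's answers until her roughly nine months are over. The documents do not support that. Section 9 makes the BWHS coordinator responsible for running the SHUTi program during the trial, and section 6.1 gives authorized personnel access to the data. The transfer sentence dates a transfer, not the first moment anyone could look. What remains is that no section assigns anyone to review diaries or answers for harm.

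**Protections exist.** The limit on restriction, the referral and the section 7.2 exclusions all reduce risk, so a reading that women are left unprotected would be wrong. None of these measures counts events.

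**The remedy is retrospective.** Correct. Questionnaire items improve the comparison between arms and the IRB summary. They do not provide oversight while restriction is in force.

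**Follow-up could affect the outcome.** Section 11.1 has the study coordinator make the assignment, and only participants are blinded. Calls prompted by positive answers before the 6-month ISI could be more frequent in one arm. This is a fair reason to keep follow-up optional and standardized.

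**Conclusion.** The point holds as a gap in described ascertainment and analysis: a recognized risk, volunteered contact as the only described route to staff, and no planned comparison of harm by arm. The 10.2 summary therefore appears to rest on volunteered reports. This is a cheap improvement, and it does not invalidate the primary analysis.

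The gain is a comparison based on the same question in every arm, with pairwise half-widths of about 7 to 13 points. It rests on 72 responders per arm, assumed frequencies of 5% to 20%, and response that is not strongly related to harm. If the attached questionnaires already contain suitable items, only the table and the basis of the 10.2 summary need to change. The documents do not establish how many harms would go unreported, or how long staff would be unaware of them.

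**What to change.** 1. **Section 9.** Unless already present, add the same four yes/no items in all three arms to the Post-Assignment and 6-month questionnaires: marked daytime sleepiness; a fall; drowsy driving or an accident; a medical visit for tiredness or sleep. Define the recall period (since starting the assigned program, then since the last questionnaire). Do not mention sleep restriction, so that participant blinding is kept.
2. **Section 12.2.** Tabulate each item by randomized arm with 95% confidence intervals and no test.
3. **Section 10.2.** Base the continuing-review summary on these counts plus volunteered reports.

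*Optional:* make the items visible to BWHS on submission, and apply the 6.1 referral through a standard message that is identical in all arms and logged by arm, because contact before the 6-month ISI could differ between arms.

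**Cost.** Four short items in two existing 45-minute questionnaires, and one table. Recall is retrospective, non-responders are missed, and real-time oversight during Cores 2 to 6 is not provided.
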